6.5. Safety Evaluations

Any clinically significant abnormalities persisting at the end of the study will be followed by the investigator until resolution or until a clinically stable endpoint is reached.

The study will include the following evaluations of safety and tolerability according to the time points provided in the TIME AND EVENTS SCHEDULE.

Adverse Events

Adverse events will be reported by the subject for the duration of the study. Adverse events will be followed by the investigator as specified in Section 9.

Clinical Laboratory Tests

Blood samples for serum chemistry (collected after an overnight fast) and hematology and urine samples for urinalysis will be collected according to the TIME AND EVENTS SCHEDULE.

The investigator must review the laboratory report, document this review, and record any clinically relevant changes occurring during the study in the adverse event section of the CRF. The following tests will be performed by the designated laboratory.

• Hematology:

- hemoglobin
- hematocrit
- white blood cell (WBC) count with differential
- platelet count
- red blood cell (RBC) count

• Serum Chemistry:

- sodium
- potassium
- chloride
- magnesium
- blood urea nitrogen (BUN)
- creatinine
- glucose (fasting)
- aspartate aminotransferase (AST)
- alanine aminotransferase (ALT)
- total bilirubin
- alkaline phosphatase
- gamma-glutamyl transferase (GGT)
- creatine phosphokinase (CPK)

- lactic acid dehydrogenase (LDH)
- uric acid
- calcium
- prolactin
- phosphorous (inorganic)
- albumin
- total protein
- cholesterol (total)
- triglycerides
- high density lipoprotein (HDL)
- low density lipoprotein (LDL)

• Urinalysis

Dipstick

- specific gravity
- pH
- glucose
- protein
- blood
- ketones
- bilirubin
- Ulli uUlli
- urobilinogen
- nitrite
- leukocyte esterase

Sediment (if dipstick result is abnormal)

- RBC
- WBC
- epithelial cells
- crystals
- casts
- bacteria

If dipstick result is abnormal, the sediment will be examined microscopically.

- In women of childbearing potential, a serum pregnancy will be performed at Screening, Day -1, Day 17 and the EOS visit (refer to the TIME AND EVENTS SCHEDULE). Additional urine pregnancy tests may be conducted throughout the study, as determined by the investigator, to establish the absence of pregnancy during the study.
- Women of non-childbearing potential and post-menopausal as defined by spontaneous amenorrhea for at least 6 months but less than 1 year will provide a blood sample for FSH testing as screening.
- Serology (HBsAg, HBcAg, hepatitis C antibody, and HIV antibodies 1 and 2) at Screening.
- Tuberculosis testing will occur at Screening.
- Urine drug screen and alcohol breath test: potential subjects will be tested for drugs of abuse (cocaine, methadone, amphetamines, cannabinoids, opiates, benzodiazepines, barbiturates, tricyclic antidepressants) and alcohol according to the TIME AND EVENTS SCHEDULE. If the results of the urine drug screen or the alcohol breath test are positive at Screening or Baseline, the subject will not be enrolled.

Vital Signs

Vital signs will include supine blood pressure, pulse, oral/tympanic temperature, and respiratory rate.

Standing and supine blood pressure and pulse will be taken after the subject has been resting quietly for 5 minutes. Blood pressure and pulse should be taken in the arm with the highest pressure, using the same arm for each reading and for all visits. An appropriately sized arm cuff will be used, and the size of the cuff should remain constant for all visits. After blood pressure has been assessed in the supine position, blood pressure will be re-measured within 3 minutes of standing).

Electrocardiogram

ECG will be recorded in triplicate (1 minute apart within 5 minutes). During the collection of ECG data, subjects should be in a quiet setting without distractions (eg, television, cell phones). Subjects should rest in a supine position for at least 10 minutes before ECG collection and should refrain from talking or moving arms or legs. If blood sampling or vital sign measurement is scheduled for the same time point as ECG recording, the ECG should be performed first, followed by vital sign measurements, and blood draws.

Three 12-lead ECGs will be recorded at a paper speed of 25 mm per second until 4 regular consecutive complexes are available. Computer-generated interpretations of ECGs should be reviewed for data integrity, reasonableness and online safety assessment.

ECGs will be overread by an ECG central reader. The following ECG intervals will be measured: RR, PR, QRS, and QT. Electrocardiogram monitoring will include the evaluation of lengthening of QTcF. A qualitative assessment of the T-wave morphology will be made by the central reader.

If a significant prolongation in QT is observed, a PK sample should be obtained.

Physical Examination

Physical examinations as well as anthropomorphic measurements (height and weight) will be performed at the times specified in the TIME AND EVENTS SCHEDULE.

Any abnormalities present at Baseline, or subsequent changes, will be documented in the

stable endpoint.

appropriate sections of the CRF. Any clinically significant abnormalities persisting at the end of the study will be followed by the investigator until resolution or until reaching a clinically

AIMS is rating scale that was designed in the 1970s to measure TD will be performed at the times specified in the TIME AND EVENTS SCHEDULE. TD is a disorder that sometimes develops as a side effect of long-term treatment with neuroleptic (antipsychotic) medications. The AIMS test is used not only to detect TD but also to follow the severity of a patient's TD over time. The AIMS test is usually given every 3 to 6 months to monitor the patient for the development of TD. For most patients, TD develops 3 months after the initiation of neuroleptic therapy; in elderly patients, however, TD can develop after as little as one month. The entire test can be completed in about 10 minutes. The AIMS test has a total of 12 items rating involuntary movements of various areas of the patient's body. These items are rated on a 5-point scale of severity from 0–4. The scale is rated from 0 = none, 1 = minimal, 2 = mild, 3 = moderate, 4 = severe. Two of the 12 items refer to dental care. The patient must be calm and sitting in a firm chair that doesn't have arms, and the patient cannot have anything in his or her mouth. The clinician asks the patient about the condition of his or her teeth and dentures, or if he or she is having any pain or discomfort from dentures.

The remaining 10 items refer to body movements themselves. The clinician or rater asks the patient about body movements. The rater also looks at the patient in order to note any unusual movements first hand. The patient is asked if he or she has noticed any unusual movements of the mouth, face, hands or feet. If the patient says yes, the clinician then asks if the movements annoy the patient or interfere with daily activities. Next, the patient is observed for any movements while sitting in the chair with feet flat on the floor, knees separated slightly with the hands on the knees. The patient is asked to open his or her mouth and stick out the tongue twice while the rater watches. The patient is then asked to tap his or her thumb with each finger very rapidly for 10–15 seconds, the right hand first and then the left hand. Again, the rater observes the patient's face and legs for any abnormal movements.

After the face and hands have been tested, the patient is then asked to flex (bend) and extend one arm at a time. The patient is then asked to stand up so that the rater can observe the entire body for movements. Next, the patient is asked to extend both arms in front of the body with the palms facing downward. The trunk, legs and mouth are again observed for signs of TD. The patient then walks a few paces, while his or her gait and hands are observed by the rater twice.

See ATTACHMENT 5: Abnormal Involuntary Movement Scale (AIMS) for an example of the AIMS.

BARS is a multiple-choice questionnaire that clinicians may use to provide an assessment of akathisia will be performed at the times specified in the TIME AND EVENTS SCHEDULE. Akathisia is a state of motor restlessness, sometimes produced by neuroleptic medication that ranges from a feeling of inner distress to an inability to sit still. The clinician or rater is instructed to observe the subject while standing and while sitting, at least 2 minutes each (total of at least 4 minutes in total). There are 4 areas where the subject is to be evaluated, 1 of these is objective, 2 are subjective, and the final is a global assessment. This scale was generated in 1989 (Barnes 1989) and was derived from the findings of studies exploring the clinical features of antipsychotic-induced akathisia both in acute psychiatric admissions and schizophrenic out-

patients on maintenance medication. Subsequently, its validity and reliability have been established, and it has been used extensively in clinical studies worldwide.

See ATTACHMENT 6: Barnes Akathisia Rating Scale (BARS) for an example of the BARS.

C-SSRS is a measure used to identify and assess individuals at risk for suicide. Questions are phrased for use in an interview format but can be completed as a self-report measure if necessary. The C-SSRS measures four constructs: the severity of ideation, the intensity of ideation, behavior, and lethality. It includes "stem questions," which if endorsed, prompt additional follow-up questions to obtain more information.

See ATTACHMENT 7: Columbia Suicide Severity Rating Scale (C-SSRS) for an example of the C-SSRS.

7. SUBJECT COMPLETION/WITHDRAWAL

7.1. Completion

A subject will be considered to have completed the study if he or she completed all required assessments at Day 19. Subjects who prematurely discontinue for any reason before completion of Day 19 will not be considered to have completed the study.

7.2. Stopping Criteria

Subjects who meet any of the following stopping criteria will be discontinued from the study:

- 2. CGI-S worsening of more than 2 points.
- 3. Suicidal ideations or behavior.
- 4. Occurrence of an AE, which could jeopardize the subject's health as per investigator opinion.
- 5. Worsening of psychotic symptoms or occurrence of any dangerous behavior against self or others as per investigator opinion.
- 6. Significant increase in ALT (ie, $> 5 \times ULN$).
- 7. Abnormal laboratory results with simultaneous increases of total bilirubin ($> 2 \times ULN$), ALT or AST ($> 3 \times ULN$) with AP ($< 1.5 \times ULN$).
- 8. Sustained mean QTcF value > 500 msec (confirmed by a second ECG under strict resting position and at minimum at 30-minute duration from the first measurement). The subject's treatment must be discontinued until mean QTcF values are obtained from the ECG central reader. If values are confirmed, the subject must be discontinued from the study; if not, the study treatment may be restarted at the discretion of the investigator.
- 9. Sustained mean increase of > 60 msec in the QTcF compared to Baseline (confirmed by a second ECG under strict resting position and at minimum at 30-minute duration from the first measurement). The subject's treatment must be discontinued until mean QTcF values are obtained from the ECG central reader. If values are confirmed, the subject must be discontinued from the study; if not, the study treatment may be restarted at the discretion of the investigator.

- 10. The subject requires treatment with another therapeutic agent that had been demonstrated to increase the QT interval or inhibit CYP2D6. In this case, discontinuation from the study should occur prior to the introduction of the new agent.
- 11. The subject experiences a syncope or severe dizziness not explained by other known causes, eg, documented orthostatic hypotension, Ménière disease.
- 12. The subject has an overt seizure or reports seizure-like activity (loss of consciousness, uncontrollable tremor not due to extrapyramidal symptoms).

The study will be stopped if 4 or more subjects are discontinued due to any of the criteria, except stopping criterion 4 if the AE is considered to be definitely not related to study drug and stopping criteron 10.

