4. STUDY POPULATION

4.1. General Considerations

Male and female CYP2D6 NM subjects, 18 to 55 years of age, inclusive, with moderate to severe negative symptoms of schizophrenia and no history of any clinically significant conditions that, in the opinion of the investigator, would jeopardize the safety of the subject or impact the validity of the study.

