4.2. Inclusion Criteria

Subjects must satisfy all the following inclusion criteria during screening to be enrolled in the study:

- 1. Subject and/or subject's legal representative, if applicable, provided informed consent prior to the initiation of any study related procedures, and the subject is judged by the investigator as being capable of understanding the study requirements.
 - 2. Male or female subject, 18 to 55 years of age, inclusive, and body mass index (BMI) < 35 kg/m² at Screening.
 - 3. Subject meets the diagnostic criteria for schizophrenia as defined in the Diagnostic and Statistical Manual of Mental Disorders-Fifth Edition (DSM-5), as established by a full psychiatric interview in conjunction with the Mini International Neuropsychiatric Interview (MINI)^a.
 - 4. Has a caregiver or family member or health care personnel who can provide information towards assessment and support the subject in terms of compliance with the protocol.
 - 5. Has documented diagnosis of schizophrenia for at least 1 year before screening into the trial.

^a Current version for DSM-5.

- 6. Subject is stable in terms of both positive and negative symptoms of schizophrenia over the last 3 months according to his or her clinician and/or a caregiver who knows the patient like the responsible person at the patient residence, a social worker, rehabilitation therapist or a caregiver/ family member or based on documentation in the clinical chart or medical records. Subjects with or without positive symptoms are allowed if these symptoms are stable for the last 3 months and they do not meet exclusion criterion 2.
- 7. Subject is currently an outpatient and has not been hospitalized for the last 3 months for acute exacerbation or symptoms worsening. Subjects who have been hospitalized for social reasons for any time period during the last 3 months or are currently hospitalized for social reasons can be included only with Sponsor's Responsible Medical Officer's approval. The social reasons must be documented in the case report form (CRF).
- 8. Subject with a score of > 20 on the PANSS original negative symptoms subscale (Sum of N1+N2+N3+N4+N5+N6+N7) at Screening and Baseline (Day -1) AND < 4 points absolute difference between the 2 visits.

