6.4. Pharmacodynamic Evaluations

The assessments will be performed at the time points indicated in the TIME AND EVENTS SCHEDULE. Every effort should be made to ensure that all clinician reported objective measurements are completed by the same individual who made the initial Baseline determinations.

CGI-S is a clinician-rated scale that is designed to rate the severity of the patient's illness at the time of assessment, including knowledge of the patient's history, psychosocial circumstances, symptoms, behavior, and the impact of the symptoms on the patient's ability to function relative to the clinician's past experience with patients who have the same diagnosis and improvement with treatment. Considering total clinical experience, a patient is assessed on severity of mental illness at the time of rating, according to: normal (not at all ill) = 1; borderline mentally ill = 2; mildly ill = 3; moderately ill = 4; markedly ill = 5; severely ill = 6; or extremely ill = 7. See ATTACHMENT Clinical Global Impression – Severity Rating (CGI-S) for an example of the CGI-S.

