ATTACHMENT ■ CLINICAL GLOBAL IMPRESSION – SEVERITY RATING (CGI-S)

Severity of illness

Considering your total clinical experience with this particular patient, how mentally ill is the patient at this time?

- 0 = Not assessed
- 1 = Normal, not at all ill
- 2 = Borderline mentally ill
- 3 = Mildly ill
- 4 = Moderately ill
- 5 = Markedly ill
- 6 = Severely ill
- 7 = Among the most extremely ill patients

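### Stopping criterion 2 (CGI-S worsening of more than 2 points) cannot be met from a reference score of 5, 6 or 7, and it names no reference assessment

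*Protocol*

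**What the plan says.** Protocol Section 7.2 opens its list with "Subjects who meet any of the following stopping criteria will be discontinued from the study". Criterion 2 reads "CGI-S worsening of more than 2 points". It carries no reference to investigator opinion and no reference visit. Criterion 9, on QTcF, does name Baseline as its comparator.

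Section 6.4 defines the scale in whole numbers from 1 (normal), with the upper anchors "moderately ill = 4; markedly ill = 5; severely ill = 6; or extremely ill = 7". The attached rating form ends at the same place, "7 = Among the most extremely ill patients", and adds a code that Section 6.4 does not have, "0 = Not assessed".

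Section 4.1 describes the population as subjects "with moderate to severe negative symptoms of schizophrenia". The severity threshold for entry in Section 4.2 is set on another scale: "Subject with a score of > 20 on the PANSS original negative symptoms subscale". Section 4.3 sets upper limits on five PANSS items and on the CDSS total. No legible criterion in either section sets a limit on CGI-S.

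The Time and Events Schedule places CGI-S at Screening, Day -1, Day 7, Day 17 and the end-of-study visit.

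Section 7.2 also stops the whole study once four subjects have been discontinued under its criteria. Two cases are not counted: criterion 4 when the adverse event is judged definitely unrelated to study drug, and criterion 10.

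**The concern.** A change-from-reference rule on a bounded scale has a ceiling: the closer a subject starts to the top, the less room there is to worsen. Criterion 2 asks for a change larger than the room left from the three highest scores. It is written as a mandatory, numeric protection for individual subjects, yet from those scores it has no effect. A subject who goes from 5 to 7, the worst rating on the scale, does not meet it.

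Subjects come off psychotropic drugs before dosing and then add olanzapine to an investigational drug, so clinical worsening is something the protocol needs to catch. Discontinuations under criterion 2 also count towards the study-level stop, and subjects with a reference score of 5 or more cannot contribute to that count through this criterion.

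The missing reference assessment is a related gap. Two sites, or two raters, could apply the criterion differently to the same ratings.

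**Working it through.** **Inputs**
- Threshold: worsening greater than 2 points (Protocol 7.2, criterion 2).
- Scale: whole numbers, maximum 7 (Protocol 6.4; CGI-S attachment). Code 0 on the form means no rating was made and is not a severity level.
- Range of reference scores: not limited by any legible entry criterion (Protocol 4.2 and 4.3).

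The documents give no figure for how often criterion 2 would be met, so there is nothing to reproduce first.

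**Step 1: smallest qualifying change.** On a whole-number scale, more than 2 means at least 3.

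**Step 2: room to worsen.** For reference score s, the largest possible worsening is 7 - s.

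**Step 3: condition.** The criterion can be met only if 7 - s ≥ 3, that is, s ≤ 4.

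| Reference score | Largest possible worsening | Later scores that meet criterion 2 |
|---|---|---|
| 1 | 6 | 4, 5, 6, 7 |
| 2 | 5 | 5, 6, 7 |
| 3 | 4 | 6, 7 |
| 4 | 3 | 7 only |
| 5 | 2 | none |
| 6 | 1 | none |
| 7 | 0 | none |

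Three of the seven scores cannot trigger the criterion, and a fourth can do so only at the scale maximum.

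**Step 4: the reference assessment.** Take a hypothetical subject rated 4 at Screening, 5 on Day -1 and 7 on Day 17. Measured from Screening the change is 7 - 4 = 3, and the criterion is met. Measured from Day -1 it is 7 - 5 = 2, and it is not. The same ratings give opposite decisions. The SAP (Section 3.2.5) defines both a Study Baseline and a Treatment Phase 2 Baseline for analysis, so the choice cannot be taken as obvious. The ceiling applies to whichever assessment is chosen.

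**Step 5: how many subjects.** The documents give no distribution of CGI-S at any visit. Among the planned 18 subjects, the number with a reference score of 5 or more could be anything from 0 to 18 (0% to 100%).

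**The case against.** The strongest reply is that worsening is covered elsewhere. Criterion 5 discontinues a subject whose psychosis worsens in the investigator's opinion, with no point threshold. Criterion 4 covers adverse events that the investigator thinks endanger the subject, and the adverse event definition in Section 9.1.1 includes aggravation of a condition present at Baseline. Section 7.3 lets the investigator withdraw a subject on clinical or safety grounds. Criteria 4 and 5 also count towards the four-subject study stop (criterion 4 unless the event is judged definitely unrelated). All of this stands. It rules out the inference that severely ill subjects have no protection or cannot contribute to the study stop.

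Criterion 1 is not legible in this copy, and it may be another symptom-based rule, even a numeric one. So a reader should not conclude that these subjects lack every numeric symptom trigger. The documents support only the loss of the CGI-S one.

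A reader might take the moderate-to-severe description to mean that most subjects would be rated 5 or more. It describes negative symptoms, not CGI-S. Subjects must also have been clinically stable for three months and are generally outpatients. No share can be derived.

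The practical effect on combination dosing is also limited. After Day 7, which precedes the first olanzapine dose, the next scheduled CGI-S is on Day 17, the last dosing day. On the planned schedule even a reachable criterion would rarely shorten coadministration.

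Two further inferences are weak. One is that no discontinuations under criterion 2 would pass for evidence of tolerability. No planned output presents that count as such, and the SAP tabulates CGI-S by treatment phase (Table 14.2.1.3) and lists it by subject (Listing 16.2.6.3), so a move from 5 to 7 would be visible. The other is that code 0 could create a false worsening. Its label says that no rating was made, and a clinician applies the rule.

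None of these replies makes criterion 2 reachable from 5, 6 or 7, or supplies its reference assessment.

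**Conclusion.** The concern holds in a limited form. Criterion 2 in Section 7.2 does not fit the scale in Section 6.4: it cannot be met from a reference score of 5, 6 or 7, and from 4 only by reaching 7. This is exact and rests only on the protocol's whole-number 1 to 7 scale. That such scores can occur at entry rests on the legible entry criteria, none of which limits CGI-S. The missing reference assessment is a separate, plain omission.

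For subjects above the ceiling, the loss is one mandatory numeric trigger and its contribution to the study-level count. Their number is unknown. Because judgement-based routes to discontinuation remain and the scheduled CGI-S ratings are sparse, this is something the sponsor should fix. It is not a defect that leaves subjects unprotected.

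**What to change.** Reconcile criterion 2 in Section 7.2 with the scale in Section 6.4, in one of two ways:
- restate the criterion so that it works for high reference scores from which worsening is still possible; or
- state that it does not apply to those scores, and name the criterion that covers those subjects.

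From a score of 7 no worsening can be recorded, so no change rule can be met there. Either version should say what covers that case. The choice of rule belongs to the sponsor's medical team, and no threshold is proposed here.

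In the same amendment, name the CGI-S assessment from which worsening is measured, and say whether it changes for Treatment Phase 2.

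The cost is a short protocol amendment, with no added visits or data. The downside is that a reachable rule may discontinue a subject who would otherwise have continued, and that discontinuation would count towards the four-subject study stop.

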- 9. Subject has discontinued psychotropic medications without risk to their clinical status or safety by Baseline. Subjects receiving treatment with long-acting or depot antipsychotic medication must have discontinued the depot antipsychotic for a full cycle of the drug (ie, 1-6 months depending on formulation).
- 10. No history of violence against self or others during the last 1 year.
- 11. Female subject, if not of childbearing potential, must be a woman who is post-menopausal (defined as spontaneous amenorrhoea for at least 1 year or spontaneous amenorrhoea for at least 6 months confirmed by follicle stimulating hormone result of \geq 40 IU/mL) or permanently sterilized (eg, tubal occlusion, hysterectomy, bilateral salpingectomy).
- 12. Female subject, if of childbearing potential, must test negative for pregnancy and must be using a 2 methods of contraception for at least 30 days after the completion of the study, one of which must be a highly effective method. The following highly effective contraception methods acceptable for this study are:
 - Surgical sterilization (for example, bilateral tubal ligation/salpingectomy, hysterectomy for female subjects or vasectomy for her male partner provided that the partner is the sole sexual partner of the female subject and that the vasectomized partner has received medical assessment of the surgical success).
 - Placement of an intrauterine device (IUD) or intrauterine system (IUS).
 - Hormonal contraception (oral, implantable, patch, injectable).
 - True sexual abstinence when this is in line with the preferred and usual lifestyle of the subject. Periodic abstinence (for example, calendar ovulation, sympto-thermal, post-ovulation methods), declaration of abstinence for the duration of the study, and withdrawal are NOT acceptable methods of contraception).

The following acceptable methods can be used as a second form of contraception during the study:

- Barrier methods for a female subject include use of an occlusive cap (diaphragm or cervical/vault caps) with spermicidal foam, gel, film, cream, or suppository.
- A male subject who has been sterilized (with medical assessment of the surgical success) or have partners of non-childbearing potential (including homosexual men) is

required to use a condom with spermicide. This is to prevent unintended exposure of the partner to the study drug via seminal fluid.

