4.3. Exclusion Criteria

Subjects meeting any of the following exclusion criteria are not to be enrolled in the study:

- 1. Current major depressive disorder, bipolar disorder, panic disorder, obsessive compulsive disorder, or intellectual disability (intellectual developmental disorder diagnosed by age 14).
- 2. Subject with PANSS item score of > 4 on:
 - P4 Excitement/Hyperactivity
 - P6 Suspiciousness/persecution
 - P7 Hostility
 - G8 Uncooperativeness
 - G14 Poor impulse control
- 3. A CDSS total score > 6.
- 4. A score of ≥ 2 on any 2 of items 1, 2, or 3, or a score of ≥ 3 on item 4 of the Barnes Akathisia Rating Scale (BARS).
- 5. Subjects with known hypersensitivity to olanzapine.
- 6. Subject's condition is due to direct physiological effects of a substance (eg, a drug of abuse or medication) or a general medical condition.
- 7. Has a current or recent history of serious suicidal behavior within the past 1 year.
- 8. Subject has a history of substance use disorder within 3 months of the Screening visit (excluding caffeine and cigarette smoking).
- 9. Positive urine drug screen for drugs of abuse (cocaine, methadone, amphetamines, opiates, benzodiazepines, and barbiturates), tricyclic antidepressants (TCA), and alcohol (except for prescription benzodiazepines). Recreation cannabinoids are allowed if the

clinician determines that the subject does not meet criteria for cannabis use disorder as defined by the Diagnostic and Statistical Manual of Mental Disorders (DSM-5) and the clinician can ensure that the subject is not using cannabis during days -2 to 17.

- 10. Subject cannot be discontinued from psychotropic medication(s).
- 11. Subject who received clozapine within 6 months of the Screening visit
- 12. Subjects is currently taking proton pump inhibitors (PPI)
- 13. Subject with a history of significant other major or unstable neurological, neurosurgical (eg, head trauma), metabolic, hepatic, renal, hematological, pulmonary, cardiovascular, metabolic, gastrointestinal, or urological disorder.
- 14. Subject with a history of seizures (subject with a history of a single childhood febrile seizure may be enrolled in this study).
- 15. Subject who has had electroconvulsive therapy (ECT), vagal nerve stimulation (VNS), or repetitive trans-cranial magnetic stimulation (r-TMS) within the 6 months prior to the Screening visit or who are scheduled for ECT, VNS, or r-TMS at any time during the study.

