6.1.1. Screening Phase

During the screening phase subjects and their legal representatives must provide written informed consent before any study evaluations are performed or any laboratory samples are collected. After written informed consent is obtained, subjects will be evaluated for study eligibility during the screening period. A complete medical history will be documented, and a complete physical examination will be conducted, including measurement of vital signs, electrocardiogram (triplicate ECG), body weight, and height. Hematology, clinical chemistry, serology, and urinalysis will be performed for all subjects, as well as verification of CYP2D6 genotype (confirmed by study-specific testing). AIMS, CGI-S, BARS, and C-SSRS will also be administered. All psychotropic drugs must be discontinued by Day -2; the time and rate of psychotropic discontinuation will be at the discretion of the investigator.

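### No entry criterion bars current suicidal ideation, yet stopping criterion 3 discontinues for any ideation, with no baseline reference, and counts toward the four-subject study stop

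*Protocol*

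**What the plan says.** **Entry.** Protocol Section 4.3, exclusion 7, repeated in the synopsis, bars a subject who "Has a current or recent history of serious suicidal behavior within the past 1 year". Section 4.2, inclusion 10, requires "No history of violence against self or others during the last 1 year". Both concern acts. No other numbered criterion mentions suicidality.

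**Assessment.** Section 6.1.1 says of Screening that "AIMS, CGI-S, BARS, and C-SSRS will also be administered". Section 6.1.3 gives the same scales on Day -1, the visit at which eligibility is confirmed. The Time and Events Schedule adds the C-SSRS on Days 1, 7, 8 and 17 and at end of study. Protocol Section 2 and SAP Sections 2 and 5.3.4 name the C-SSRS as the instrument for suicidal ideation.

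**Stopping.** Section 7.2 opens: "Subjects who meet any of the following stopping criteria will be discontinued from the study". Criterion 3 is "Suicidal ideations or behavior". The section then says that "The study will be stopped if 4 or more subjects are discontinued due to any of the criteria". The only exceptions are criterion 4, when the adverse event is definitely unrelated to study drug, and criterion 10.

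**Analysis.** SAP Section 5.3.4 summarizes the C-SSRS as observed values and as change from both the Study Baseline and the Treatment Phase 2 Baseline.

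**The concern.** The entry rules and the stopping rule treat the same state differently. Ideation is enough to remove a subject once in the study, but it is not named as a reason to keep that subject out.

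Two things are at stake. The first is subject protection. These are people with schizophrenia who are taken off psychotropics to take part, and Section 12.1 says that they will receive no benefit. The second is what the four-subject stop measures. It is a safety rule for the drug combination, but as worded it can also count a condition that predates the first dose.

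**Working it through.** This is a comparison of texts. The plan gives no figure on this point beyond the threshold of four, so there is nothing to reproduce.

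**1. Entry criteria.** Section 4.2 has 14 inclusion criteria and Section 4.3 has 28 exclusion criteria: 14 + 28 = 42. Read one by one, 0 of 42 name suicidal ideation or a C-SSRS result.

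**2. Wording of the stopping list.** Where the authors meant change, they wrote change. Criterion 2 is "CGI-S worsening of more than 2 points". Criterion 9 is "Sustained mean increase of > 60 msec in the QTcF compared to Baseline". Part of criterion 5 is a worsening of psychotic symptoms. Criterion 3 has no such qualifier.

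**3. Stopping criteria set against entry criteria.**

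| Stopping criterion | Entry counterpart |
|---|---|
| 8, QTcF above 500 msec | Exclusion 21, QTcF limits |
| 10, QT-prolonging or CYP2D6-inhibiting drug needed | Exclusions 19 and 20 |
| 11, syncope | Exclusion 25 |
| 12, seizure | Exclusion 14 |
| 3, suicidal behavior | Exclusion 7 (serious behavior) |
| 3, suicidal ideation | None |

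The pattern is not universal. The liver criteria (6 and 7) have no general numeric entry limit, only investigator-judged exclusion 16.

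**4. One subject traced through.** Take a subject who answers yes to ideation item 1 (wish to be dead) at Screening, unchanged on Day -1. The subject has no suicidal behavior, no current major depressive disorder, a CDSS total of 6 or less, and meets everything else.

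- Sections 4.2 and 4.3: no numbered criterion excludes on ideation.
- Section 6.1.1: psychotropics stopped by Day -2. Section 6.1.2: admitted on Day -2.
- Day 1: first dose of roluperidone.
- Day 7: the C-SSRS is given after a week of dosing, with the same answer. Criterion 3 as worded is met and discontinuation is mandatory.
- Criterion 3 is not among the exceptions, so the subject is 1 of the 4. Then 4 − 1 = 3 further discontinuations stop the study.

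The schedule does not say whether the Day 1 C-SSRS comes before or after the dose, so the trace relies on Day 7.

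**5. What an entry check could avert.** A check at Screening can avert washout and admission. A check on Day -1 comes after both, so it averts only dosing and the count. Screening runs from Day -28 to Day -3, so a Day -1 question covering the time since Screening looks back 2 days (Day -3 to Day -1) to 27 days (Day -28 to Day -1).

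**The case against.** **Investigators would keep such subjects out anyway.** Often they would. Section 4.1 leaves room for judgment on conditions that endanger the subject. Inclusion 6 asks for three months of stable symptoms, and inclusion 9 for psychotropic withdrawal without risk to safety. Exclusion 1 removes current major depressive disorder and exclusion 3 removes a CDSS total above 6. An investigator could also use the Day -1 C-SSRS when judging inclusion 9 or exclusion 7, so it would go too far to say that the C-SSRS plays no part in eligibility. What stands is that these safeguards are discretionary or indirect. None is a rule on ideation.

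**Criterion 3 may mean ideation that emerges on treatment.** That is a natural reading of a stopping list, but the text does not say it, and its neighbors show how the authors worded change when they meant it.

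**Section 7.2 gives no start time, so criterion 3 could apply before the first dose.** This too is possible and unstated. If applied on Day -1 it would prevent dosing, but washout and admission would already have happened, and it would be unclear whether the subject counts toward the four.

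**Discontinuing for any ideation is the cautious choice, and subjects are inpatients.** Agreed. That is a reason to leave criterion 3 alone and to act at entry.

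**Criterion 3 does not name the C-SSRS.** Also true. The link is that the C-SSRS is the only instrument that the documents name for suicidal ideation. Attachment 7 shows an example Baseline/Screening form; the on-treatment form is not shown.

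**Conclusion.** The gap is real on the text. Under the numbered criteria a subject with current ideation is eligible, and may be washed out, dosed, discontinued and counted for a state that was there before treatment. This rests on reading criterion 3 as worded, without an implied restriction to new ideation.

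The size is one of four counts per such subject. How many there would be is unknown; probably few, given the safeguards above.

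A reader might infer three stronger things that the documents do not support:

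- *That the study is at material risk of stopping for this reason.* The documents give neither the share of enrolled subjects with ideation at entry nor the rate of other counted discontinuations. Any stop probability would be built on invented inputs, so none is claimed.
- *That the PK comparison is compromised.* It is not. Section 7.3 also lets the sponsor replace subjects who withdraw.
- *That the stopping rules are wrong and should be loosened.* Nothing here shows that. The mismatch can be closed at entry.

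The point is a cheap improvement to subject safety.

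**What to change.** Extend exclusion 7, in Section 4.3 and in the synopsis, with a clause such as: *or current suicidal ideation, meaning a yes to any C-SSRS ideation item (1 to 5) that is current at the Screening visit or, on Day -1, has occurred since the Screening visit; lifetime ideation, or ideation that had resolved before Screening, does not count.* Any item is the right level because criterion 3 is now triggered by any ideation. If criterion 3 were ever given a severity level, the entry clause should take the same one.

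State the look-back on the form. The Screening form in Attachment 7 leaves the number of past months open; fill in a short period that matches *current*. The Day -1 form needs a question covering the time since Screening, which the attached example does not show.

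Leave criterion 3 and the four-subject stop unchanged.

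**Cost.** One clause in two places, made by protocol amendment with the IRB approval that Section 13.1 requires, and the look-back entries on the forms. No assessment is added, because the C-SSRS is already given at both visits. The downside is possibly a few more screen failures.
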